d. Sample Size Estimation. Based on our power estimates, a sample of 75 women per group will be needed for a final sample of 150 women. We have planned for a conservative attrition (15%) which is higher than our Sunshine pilot (8%) but consistent with our SWEEP trial (59). **Therefore, 180 (90 per group) will be enrolled into the treatment arms.** Thus far, out of 169 patients enrolled, only 83 (49%) have been randomized to treatment arms. Thus, we will enroll 360 as we have had a screen failure of almost 50% to allow for a sufficient number of persons to be randomized. For the power analysis, we used a repeated measures approach formulae developed by Hedeker et al. (158) which allows comparisons of the group means across time while adjusting for baseline values and accounting for the correlation between baseline and follow-up observations. We have assumed a 2 tailed test with a type I error rate of 0.05 for each outcome. **Depression:** There was a 14 point decrease in depression from baseline to 6 months following vitamin D supplementation using the CES-D (see pilot data). Using the control group in the SWEEP study (which had the same enrollment criteria for depression and did not receive treatment), there was a 7 point decrease in depression (28.8 to 21.4) as depression symptoms can improve without treatment. Given these group difference, the effect size is .46. A sample size of 30 per group would provide 95% power. We also powered for depression remission (CED-D < 16) as other depression trials (159). In our vitamin D study, 55% of women had remission of their depression at 3 months and 63% at 6 months. Using the control group data from the SWEEP study, 30% had remission of depression at 3 months and 20% at 6 months. Having this information, a sample size of 75 per group (n=150) would be needed to detect differences in depression remission at 3 months and a sample of 25 per group (n=50) to see the difference at 6 months. **Diabetes Self-Management:** There were significant differences from baseline to six months (see pilot data) to calculate the effect sizes. We calculated an effect size of .70 for diabetes distress and .33 for self-care. For diabetes self-efficacy, an effect size of .30 based on our previous research (SWEEP) will be used. A sample of 75 per group (n=150) will achieve 85% power on these study outcomes. **Blood Pressure:** We observed a decrease of 8 mmHg in the vitamin D study but no change in a control group from the SWEEP study (136.2 mmHg to 135.9 mmHg). Pfeifer et al. (96) reported a 7% decrease in blood pressure in women after 800 IUs of D₃ for 6 weeks. To be conservative, we will assume a difference of about 5 mmHg to account for the placebo effect and regression to the mean phenomena commonly observed in clinical trials. This difference yields an effect size of about 0.3. A final sample of 150 (75 per group) would provide 80% power to assess this outcome. **Inflammation (Exploratory):** Using pilot data of [name] (see pilot data) a sample size of 75 per group provides 85% power to detect differences between groups on depression and inflammation. **For the meditational analyses,** power was estimated using effect sizes from our previous research and current pilot study. Although the depression effect sizes discussed above are large (160), a more conservative approach anticipating medium effect sizes was employed for the mediation analysis. With medium effects for self-care outcomes, a total sample of 135 would achieve 95% power.

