
Sample size estimation:

For the sub-study (FAMDD), the qualitative component of the study, the sample size proposed was 50 women. For the quantitative component, it is estimated that since these tools have been used previously, that the estimate needed for adequate power will be determined by power analysis. An a-priori sample size by these investigators for multiple regression indicates with a medium effect size, $p = .05$, power of .80 and up to 6 independent variables a minimum sample of 97 will be needed for quantitative analysis.

6. Potential Problems and Alternative Solutions. Although subject accrual is a concern for all research, we have been successful in our previous studies. We have established relationships with key clinical sites (see diabetes educators, physicians support letters) which have reported a high volume of accessible patients (see

2b, recruitment table). Although attrition is another potential issue, it has been low in our previous studies (6% pilot vitamin D, 15% SWEEP). And, we have provided steps for addressing adherence, retention, and drop-outs (see 3d). To prevent measurement issues, protocols for training of staff to ensure consistency with the collection of data have been established in our prior work. It is possible that factors like diet and sunshine may impact on vitamin D levels. Although the impact of these variables in our pilot work was not substantial, they will be measured. Because body fat may affect vitamin D levels, body composition has been added as measurement. Treatments will be assessed at all time points and evaluated for their contribution to the study outcomes. In our prior work, we did not see significant changes in medications as women were on established medications prior to enrollment. The placebo effect may have been a factor for the positive findings in our one-arm pilot study; hence a randomized trial is the next logical step. Study staff will be blinded to the treatment and we have protocols if the blind needs to be broken (see 1c-e). Staff will not provide additional support to the patient for treatment; however, protocols for increased depression have been delineated (3b). Finally, it is possible that if depression improves, self-management may not. Therefore, the next planned study would be a randomized trial to see if treating depression with vitamin D prior to diabetes self-management education could enhance learning and self-management outcomes.

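### The depression planning differences carry no placebo allowance, although blood pressure gets one; 3-month remission, the only depression calculation that needs 75 per group, is sensitive to this

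*Combined protocol and SAP*

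**What the plan says.** All planning figures are in section V.5.d, under a common error rate: "We have assumed a 2 tailed test with a type I error rate of 0.05 for each outcome".

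- **CES-D score.** The pilot fell by 14 points from baseline to 6 months. The SWEEP controls, who were untreated, fell by 7. The plan reports an effect size of .46 and says that 30 per group gives 95% power.
- **Remission, treatment side.** "In our vitamin D study, 55% of women had remission of their depression at 3 months and 63% at 6 months".
- **Remission, control side.** "Using the control group data from the SWEEP study, 30% had remission of depression at 3 months and 20% at 6 months".
- **Resulting numbers.** "a sample size of 75 per group (n=150) would be needed to detect differences in depression remission at 3 months". For the 6-month comparison the plan asks for only 25 per group. No power is stated for either.
- **Overall.** "a sample of 75 women per group will be needed for a final sample of 150 women". With attrition, 90 per group are randomized.
- **Blood pressure.** The pilot fell by 8 mmHg and the SWEEP controls did not change. The plan then writes: "To be conservative, we will assume a difference of about 5 mmHg to account for the placebo effect and regression to the mean phenomena".

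Section V.6 adds: "The placebo effect may have been a factor for the positive findings in our one-arm pilot study". Section V.1 describes a double-blind comparison of 50,000 IU with 5000 IU weekly. Both arms have the same reminders, calls and visits.

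**The concern.** The planning contrast is known treatment against no treatment, taken from two separate studies. The trial's contrast is one blinded vitamin D dose against another, with the same attention in both arms. Any placebo response, and any effect of the lower dose, would appear in the comparator arm and narrow the difference. The SWEEP controls cannot show how large that response is, because they took no capsule.

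The plan accepts this reasoning for blood pressure, an exploratory outcome read by machine. It does not apply it to the primary outcome, a self-reported mood score, or to remission derived from that score, and it gives no reason for the difference. At stake is how a null result at 3 months would be read: as evidence against an effect, or as the product of an optimistic planning difference.

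**Working it through.** **1. Reproduce the plan's remission figure.** Inputs from V.5.d: 55% v 30%, 75 per group, two-sided 0.05. With p̄ the mean of the two rates,

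power = Φ{ [ |p1 − p2|·√n − 1.96·√(2p̄(1 − p̄)) ] / √(p1(1 − p1) + p2(1 − p2)) }.

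Here p̄ = 0.425, so (2.165 − 1.96 × 0.699) / 0.676 = 1.175 and power is 88.0%. Solving for n at 88% power returns 75. With a continuity correction or Fisher's test, power at 75 is about 86%. For 6 months, 63% v 20% at 25 per group gives 89.5%. Both of the plan's numbers are therefore consistent with roughly 88% to 90% power.

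**2. Shrink the difference.** Hold the control rate at the plan's value and keep a fraction r of the difference, at 75 per group:

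| r | 3-month rates | Power | 6-month rates | Power |
|---|---|---|---|---|
| 1 | 55% v 30% | 88% | 63% v 20% | >99% |
| 0.90 | 52.5% v 30% | 81% | 58.7% v 20% | >99% |
| 0.80 | 50% v 30% | 71% | 54.4% v 20% | >99% |
| 0.70 | 47.5% v 30% | 60% | 50.1% v 20% | 98% |
| 0.625 | 45.6% v 30% | 51% | 46.9% v 20% | 94.5% |
| 0.50 | 42.5% v 30% | 36% | 41.5% v 20% | 82% |

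The row r = 0.625 is the blood-pressure ratio, 5/8. Around that row, 3-month power runs from 45% (Fisher's test) to 54% (ratio 5/7.7, net of the 0.3 mmHg SWEEP change). Raising the control rate instead (55% v 39.4%) gives 48%. With all 90 randomized women per group evaluable, 45.6% v 30% gives 58%.

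**3. CES-D score.** The plan does not say what .46 is. A 7-point difference over the pilot SDs is 7/7.6 = 0.92 down to 7/8.9 = 0.79, and 0.92 is twice .46. Two readings follow, using two-sample t-test power with noncentrality d·√(n/2).

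- *The difference is 7 points over a pilot SD.* At d = 0.92 and 30 per group, power is 94%, close to the stated 95%. After a 5/8 cut (d = 0.575) it is 59%. At 75 per group after the cut, power is 85% (d = 0.79 × 0.625 = 0.49) to 94% (d = 0.575).
- *.46 is itself a standardized mean difference.* At 30 per group, power is 42%. At 75 per group it is 80%, falling to 42% after the cut (0.46 × 0.625 = 0.29). Adjusting for baseline and averaging two follow-ups multiplies the variance by (1 + ρ)/2 − ρ², which is 0.56, 0.50 and 0.36 for assumed correlations ρ of 0.3, 0.5 and 0.7. Power after the cut is then about 65%, 70% and 83%.

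**The case against.** The strongest reply is that 5/8 is not the plan's discount for depression. For blood pressure it covers placebo effect and regression to the mean together, and there the SWEEP subtraction removed almost nothing (136.2 to 135.9 mmHg). For depression the subtraction already takes 14 points to 7, which removes spontaneous improvement and at least part of regression to the mean. Applying 5/8 again may count some of this twice. That stands. A reader might infer that the plan's own logic sets 3-month remission power at 51%. The documents do not support that; they give no size for the placebo component in depression, so only a range can be shown.

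A reader might also infer that the primary analysis is underpowered. That does not follow either. The primary test is the group-by-time interaction in a mixed model of depressive symptoms (V.5.b), and that section specifies no remission analysis. Nor does 3-month remission alone fix the sample size: self-management, blood pressure and inflammation are also quoted at 75 per group. Six-month remission keeps most of its power at 75.

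What remains is that the subtraction allows for improvement without treatment, not for improvement on a blinded capsule with regular contact.

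**Conclusion.** The concern holds as an inconsistency in the planning assumptions with a bounded effect. The depression differences carry no placebo allowance, and the plan gives no reason for treating them differently from blood pressure. Three-month remission is the only depression calculation that needs 75 per group. Keeping 80% of its difference already gives 71% power; keeping half gives 36%. These figures assume the SWEEP rate for the control arm, 75 evaluable women per group and an uncorrected two-proportion test. The 88% starting point is implied by the plan's numbers, not stated in it. Six-month remission stays at 82% or more over the same range.

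For the CES-D score no single replacement figure is safe until .46 is defined. The statement of 95% power with 30 per group is not robust: it nearly reproduces only at d = 0.92 with no discount.

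**What to change.** Amend V.5.d; the sample size does not change.

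1. State depression power at 75 per group over an explicit range of placebo discounts, for remission at both times and for the CES-D score. Say that the size of the discount is an assumption.
2. Say that 3-month remission is not robustly powered, and treat it as supportive.
3. Define the .46: which difference, which SD, and whether it is a standardized mean difference. Then restate CES-D power as a range; do not substitute a single figure such as 90%.
4. Remove the sentence on 30 per group, or qualify it with the effect size and the absence of a discount.

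The cost is text only, with no added patients. The downside is that the stated depression power becomes less favourable.

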Depression and Self-Management. We also observed an improvement in diabetes self-management (specifically, self-care behaviors and diabetes distress) in our pilot study. We believe that this effect was due to an improvement in depression. Evidence indicates that depression negatively impacts diabetes self-management (72-76), especially for women (6). Self-management includes beliefs (i.e., self-efficacy), emotional responses (i.e., diabetes distress), as well as the ability to engage in self-care behaviors (diet, activity, medication adherence) (77). For women, depression is associated with lower self-efficacy (78, 79) and increased diabetes distress (80, 81), both of which can contribute to poor self-care behaviors (82). Although there is significant research to indicate that depression impacts diabetes self-management, there is limited evidence as to whether treatment of depression improves diabetes self-management (13-15). This study will add to that body of knowledge. For this study, we propose that if vitamin D supplementation reduces depression, self-management will improve as individuals begin to feel better and more actively participate in their care. If depression subsides, we believe that self-efficacy, diabetes distress, and self-care behaviors will improve (Figure).

Vitamin D and High Blood Pressure. We also observed an improvement in blood pressure in our pilot study. Definitive mechanistic studies of vitamin D and blood pressure are currently in progress. Both in vitro and in

vivo studies of vitamin D receptor knockout mice have supported the hypothesis that Vitamin D may affect blood pressure by regulating activity of the renin-angiotensin system through suppression of renin biosynthesis (40, 44). Vitamin D may also be effective in reducing deleterious effects of glycation end products on the endothelium (41), thus allowing for endothelium-dependent vascular relaxation (42, 43).

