concerns with the supplementation and to ensure that their depression did not worsen (and it did not). Women were then seen at three months for follow-up measures and for prescription refill. For all 3 time points, patients completed questionnaires that included: depression (CES-D) and diabetes self-management which included diabetes self-care inventory (SCI) and diabetes distress using the Problem Areas in Diabetes Scale (PAIDS). For the pilot study, labs and physical measurements were also assessed and included vitamin D, calcium, PTH, HbA1c, blood pressure, and weight. Depression was verified at baseline using the Diagnostic Interview Schedule (DIS). Following completion of the study, all patients were given their labs and referred to their healthcare provider for future follow-up.

Repeated measures ANOVA results indicated that depression symptoms decreased significantly over time. In addition, there was a significant improvement in self-care behaviors and less diabetes distress. Vitamin D levels increased to a therapeutic level, and there were no significant changes in labs (calcium and parathyroid hormone). Although there was no improvement in HBA1c, the average baseline value indicated very good control (<7%). Other investigators have reported no change in HBA1c with vitamin D supplementation (97-98). A clinically and statistically significant decrease in systolic blood pressure was observed. There was also a small decrease in weight.

Variables	Baseline Mean (SD)	Three Months Mean (SD)	Six Months Mean (SD)	P value
Depression-CES-D	26.83 (7.6)	15.13 (8.9)	12.15 (8.3)	<.001
Self Care (SCI)	2.76 (.58)	2.87 (.57)	2.88 (.64)	.041
Distress (PAIDS)	29.00 (14.2)	21.29 (14.4)	19.36 (14.9)	.001
Vitamin D (ng/ml)	18.78 (7.0)	34.39 (9.4)	37.5 (9.5)	<.001
Systolic BP (mmHG)	140.43 (17.1)	135.04 (17.1)	132.46 (14.3)	.007
Weight (pounds)	226.10(59.0)	224.64 (59.9)	223.58 (59.4)	.026

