Hypothesis 1: Women receiving 50,000 IUs vitamin D supplementation will report fewer depressive symptoms (primary outcome), increased diabetes self-management mediated by depression improvement (secondary outcome), and have a lower systolic BP (exploratory) compared to those 5000 IUs at three and six months follow-up.

For analysis of the primary outcome (depressive symptoms) generalized, linear, mixed models (GLMM) for repeated measures will be used (154). The proposed model will have one between-subjects variable GROUP (vitamin D supplementation; control) with two levels and one within-subjects variable TIME with three levels (baseline, 3 and 6 months). The test of the hypotheses will hinge on the GROUP by TIME interaction as an indication of group differences in the variable of interest over time. A given hypothesis will be supported with the finding of a statistically significant GROUP by TIME interaction, and the finding that the means are in the hypothesized direction. GLMM will be implemented using SPSS which will provide estimates of the means for each outcome variable by time and treatment groups. The results will be summarized with adjusted means and 95% confidence intervals. A compound symmetric covariance structure will be assumed. If necessary, other covariance structures, such as Huynh-Feldt, will be investigated. An intention-to-treat analysis (ITT) which includes an analysis of completers and noncompleters will also be done using GLMM. Stratification by depression severity should provide comparable groups at baseline; however, differences will be assessed. All analyses will control for baseline values of body composition (body fat), race (white compared with nonwhite), and time at entry into the study (as season of the year, winter, summer, spring, fall) as previously done by our consultant, [name], in his vitamin D trials. Other covariates, related to diabetes (length of time with diabetes, HBA1c), lifestyle factors, (physical activity, diet), and previous depression will be added to generate a multivariate model which is parsimonious and based on the clinical relevance and statistical significance of these factors.

For analysis of the secondary outcome (self-management), regression analysis will be used to test whether an improvement in self-management is mediated by an improvement in depressive symptoms (Figure). The Preacher and Hayes macro add-on for SPSS will be used. This technique estimates the path coefficients and

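### The diabetes distress effect size of .70 is an uncontrolled before-after change used as a between-arm effect, so the stated 85% power depends on how much the low-dose arm improves

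*Combined protocol and SAP*

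**What the plan says.** The Diabetes Self-Management part of Sample Size Estimation (V.5.d) derives its effects from the pilot's change between baseline and six months: "There were significant differences from baseline to six months (see pilot data) to calculate the effect sizes. We calculated an effect size of .70 for" (the sentence goes on to name distress, and gives .33 for self-care). Self-efficacy is given .30 from the earlier SWEEP trial. The power claim covers all three: "A sample of 75 per group (n=150) will achieve 85% power on these study outcomes". The error rate is set for every outcome: "We have assumed a 2 tailed test with a type I error rate of 0.05 for each outcome". The section names a repeated-measures formula that adjusts for baseline and uses the baseline to follow-up correlation, but prints no correlation.

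Preliminary Studies (IV) describes the pilot as a one-group pre-post study. Its results table gives distress at baseline, three and six months, with the p value, as: "Distress (PAIDS) 29.00 (14.2) 21.29 (14.4) 19.36 (14.9) .001".

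For depression, V.5.d uses the untreated SWEEP control group: "there was a 7 point decrease in depression (28.8 to 21.4) as depression symptoms can improve without treatment". For blood pressure it reduces an observed 8 mmHg to about 5 mmHg, citing placebo effect and regression to the mean. No such step appears for distress or self-care.

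**The concern.** The trial compares 50,000 IU with 5000 IU, so the relevant effect is the difference in change between two randomised arms. A before-after change in a single treated group equals that difference only if the comparison arm does not change. The plan does not argue this for distress, and its own reasoning points the other way. Significance (I) says of the pilot's self-care and distress gains: "We believe that this effect was due to an improvement in depression". V.5.d then records that untreated women also improved on depression. Potential Problems (V.6) accepts that a placebo effect may have contributed to the pilot's results.

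At stake is how a null distress result would be read. Against an 85% power claim it looks like evidence of no effect. If part of the .70 would also occur in the low-dose arm, the trial has less power for the net difference than the text suggests.

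**Working it through.** **Inputs from the documents.** PAIDS 29.00 (SD 14.2) at baseline, 21.29 at three months and 19.36 (SD 14.9) at six months; 75 per arm; two-sided 0.05. SWEEP control CES-D 28.8 to 21.4; pilot CES-D 26.83 to 12.15.

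**Assumptions.** One common correlation r between visits (none is printed) and SD 14.55, from √((14.2² + 14.9²)/2).

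**1. Where .70 comes from.** The fall is 29.00 − 19.36 = 9.64 points. 9.64/14.2 = 0.68 and 9.64/14.55 = 0.66. A value of exactly .70 needs an SD of 9.64/.70 = 13.77. Read as an SD of change, this implies r = (14.2² + 14.9² − 13.77²)/(2 × 14.2 × 14.9) = .55. On either reading, .70 is the whole uncontrolled fall.

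**2. The plan's power figure.** For a two-sample t test with noncentrality d√(75/2), power is 98.9% at d = .70, 52% at .33 and 45% at .30. None of these is 85%. With baseline adjustment and two follow-ups, .30 reaches 85% at r of about .68, so the joint claim is attainable only with a correlation the plan does not state.

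**3. How much low-dose improvement the 85% tolerates.** 85% power needs d = 0.4925. The effective SDs are:
- change scores: SD of change 13.77;
- baseline-adjusted, month 6: 14.55 × √(1 − r²);
- baseline-adjusted mean of months 3 and 6: 14.55 × √((1 + r)/2 − r²).

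At r = .55:

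| Analysis | Effective SD | Difference needed (0.4925 × SD) | Tolerable improvement |
|---|---|---|---|
| Change scores | 13.77 | 6.78 | 9.64 − 6.78 = 2.86 |
| Adjusted, month 6 | 12.16 | 5.99 | 9.64 − 5.99 = 3.65 |
| Adjusted, months 3 and 6 | 10.00 | 4.93 | 9.64 − 4.93 = 4.71 |

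The last row sets the full month-6 fall against the two-visit mean. The pilot fall averaged over the two visits is (7.71 + 9.64)/2 = 8.68. With that, the tolerable improvement is 8.68 − 4.93 = 3.75, or 3.75 × 9.64/8.68 = 4.2 on the month-6 scale. At r = .75 the adjusted figures are 9.64 − 4.74 = 4.9 (month 6) and up to 9.64 − 4.01 = 5.6 (two visits).

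**4. If the low-dose arm improves by half.** The control share for depression is (28.8 − 21.4)/(26.83 − 12.15) = 7.4/14.68 = 0.50. Half of 9.64 leaves 4.82 points; half of the averaged fall leaves 4.34. Power at r = .55:
- change scores, 4.82/13.77: 57%;
- adjusted, month 6, 4.82/12.16: 67%;
- adjusted, months 3 and 6: 75% for 4.34/10.00, 83% for 4.82/10.00.

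Adjusted power reaches 85% from r of about .58 (two visits, 4.82), .69 (two visits, 4.34) or .74 (month 6).

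**5. Self-care.** The pilot change is 2.88 − 2.76 = 0.12, and 0.12/0.58 = 0.21, not .33. The .33 may rest on an SD of change that is not printed. It comes from the same uncontrolled change and has far less margin.

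**The case against.** A reader might infer that the 85% fails once the low-dose arm improves by 2.9 points, or that the trial is plainly underpowered for distress. The documents support neither.

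- **Method.** The 2.9 belongs to unadjusted change scores. V.5.d names a baseline-adjusted repeated-measures method, which tolerates more.
- **Correlation.** The value .55 is back-solved from .70. At r of about .68, the value that makes the 85% hold for .30, power at half improvement over two visits is about 84% for 4.34 points (4.34/8.94) and 91% for 4.82 (4.82/8.94).
- **Half improvement.** This share is borrowed. CES-D was an enrolment criterion, so its control fall is exposed to regression to the mean from selection; PAIDS was not. The SWEEP controls barely moved on blood pressure (136.2 to 135.9 mmHg).
- **Planned analysis.** The sentence "The test of the hypotheses will hinge on the GROUP by TIME interaction as an indication of group differences in the variable of interest over" (cut short here) sits in the primary-outcome paragraph of V.5.b. Self-management is analysed by mediation regression, powered separately on medium effects with 135 women in total.
- **Importance.** Distress has the most slack of the three components, and the three-month remission calculation independently requires 75 per group.

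All of this stands, and it limits the size of the problem. It does not change where .70 came from, or the fact that the 85% sentence applies it to two arms. The mediation calculation is a separate claim and does not repair that one.

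**Conclusion.** The planning figure is wrong as written: .70 is the pilot's full uncontrolled change, and using it between arms assumes no low-dose improvement, which is inconsistent with how the same section treats depression and blood pressure. The 85% is conditional, not refuted. It holds while the low-dose arm improves by less than roughly 3.7 to 4.7 points under baseline adjustment at r = .55, and by more at higher r. A shortfall at half improvement rests on two things the documents do not supply: a control-arm distress change and a correlation. Severity is minor to moderate: one component of a secondary outcome is affected, and N does not depend on it. Self-care shares the fault with less margin.

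**What to change.** In Sample Size Estimation (V.5.d), stop presenting .70 as a between-arm effect. Give the distress planning difference as the pilot change minus an expected low-dose change, taken from SWEEP control distress data if held and otherwise shown over a range. Print the SD and correlation used. Restate the 85% as holding for a named minimum between-arm difference under the baseline-adjusted method; at r = .55 and SD 14.55 that is about 6.0 points at month 6, or 4.9 for the mean of months 3 and 6. Correct self-care (.33) in the same way and show how it follows from the pilot table.

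The cost is one rewritten paragraph and a short recalculation, with N unchanged. The stated power for distress and self-care may look less favourable.

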Pilot study description and findings. Using this preliminary data from SWEEP, we applied and were funded for a "proof of concept study" to examine whether vitamin D supplementation in women with 2 diabetes with low Vitamin D levels could improve depression and metabolic outcomes (NIH 5P60DK020595 pilot study, University of Chicago Diabetes Research and Training Center). It was branded as the "Sunshine Study". A one-group pre-post test design study was used to test for feasibility, compliance, and the impact of vitamin D₂ supplementation. Weekly ergocalciferol (D₂) of 50,000 IUs was administered for six months. This formulation of vitamin D is approved for the treatment of low vitamin D, and was being used at our clinical practice site at the time of the study. Women were enrolled if they had: type 2 diabetes greater than 6 months, significant depressive symptoms (CESD ≥ 16), were not taking vitamin D supplements or had stopped them for at least 1 month prior to enrollment, had a vitamin D level < 30 ng/ml, and were not hypercalcemic. These same inclusion and exclusion criteria are being proposed in this study. Over 300 women were phone screened for participation. Fifty women were enrolled at baseline. They were a mean age of 55 years, had diabetes an average of 8 years with a mean HBA1c of 6.8%, and 60% were white. At three months, 49 or 98% continued and at six months, 46 or 92% were retained. Procedures for dispensing the vitamin D and follow-ups are the same being proposed for this study (see procedures). Women came within 10 days following baseline screening to obtain their prescription of vitamin D, were then sent a weekly message (their preferred method as phone, text, or e-mail) to take their vitamin D, and called at 4 to 6 weeks. This was done to determine if any

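### The 85% power stated for self-care does not follow from the pilot change it is said to come from, which gives about 22–40% at r = .5 and 56–71% at r of about .83

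*Combined protocol and SAP*

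**What the plan says.** Section V.5.d (Sample Size Estimation) takes the distress and self-care effects from the pilot: "There were significant differences from baseline to six months (see pilot data) to calculate the effect sizes". It then reports: "We calculated an effect size of .70 for diabetes distress and .33 for self-care". Self-efficacy is given .30 from the earlier SWEEP trial. All three share one power statement: "A sample of 75 per group (n=150) will achieve 85% power on these study outcomes".

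The method is described as a repeated-measures formula that compares group means "while adjusting for baseline values and accounting for the correlation between baseline and follow-up observations". No correlation is printed for any outcome, and the SD used to standardise the effects is not named.

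The pilot table in Section IV gives self-care as 2.76 (.58) at baseline, 2.87 (.57) at three months and 2.88 (.64) at six months, p = .041. The pilot had one arm, and "at six months, 46 or 92% were retained".

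The same section treats other outcomes differently. For CES-D it sets the pilot's 14-point fall against a 7-point fall in an untreated control group. For systolic blood pressure it reduces an observed 8 mmHg: "To be conservative, we will assume a difference of about 5 mmHg to account for the placebo effect and regression to the mean". Section V.6 adds: "The placebo effect may have been a factor for the positive findings in our one-arm pilot study". No such allowance is made for self-care.

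**The concern.** The printed effect is more than one and a half times what the cited source shows in ordinary SD units, and the power attached to it is well above what the pilot change gives. Self-management is the named secondary outcome, and self-care behaviours are one of its three components. A null self-care result would be read against a stated 85% chance of detecting the pilot effect, so a low-power null could be taken as evidence of no effect. Because one percentage covers three outcomes with very different effects (.70, .33, .30), a reader cannot see which of them is weak.

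**Working it through.** **Inputs.** 75 per group, two-sided 0.05 (Section 5.d); pilot self-care means and SDs, p = .041, 46 women at six months (Section IV); compound symmetry (Section 5.b). Assumed throughout: the comparison arm does not change, which favours the plan. SD .58 is used unless stated.

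**1. The plan's figure.** A plain two-sample t test with 75 per group gives 99% for .70, 52% for .33 and 45% for .30. With a baseline-adjusted mean of the two follow-up visits, whose variance factor is (1+r)/2 − r², .33 reaches 85% at r of about .59 and .30 at r of about .69. The blanket 85% can therefore be reached from the printed effect sizes, but only with an unstated r of about .69.

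**2. Does .33 match the pilot?** The change is 2.88 − 2.76 = 0.12. Then 0.12/.58 = .207 and 0.12/.64 = .188.
- As a raw-SD effect, .33 × .58 = 0.19 points, and 0.19/0.12 is about 1.6 times the pilot change.
- As a standardised change, 0.12/.33 = .364. The SD of change is √(.58² + .64² − 2r × .58 × .64), which is .363 at r = .827. The correlation is then already inside the .33, and a between-arm comparison of change has power 52% (noncentrality .33 × √37.5 = 2.02).

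**3. What r does the pilot imply?** The pilot p values come from a repeated-measures ANOVA ("Repeated measures ANOVA results indicated that depression symptoms decreased significantly over time"). For self-care, p = .041 on 2 and 90 df gives F = 3.31.
- Between-time mean square: 46 × .00443 = .204.
- Error mean square: .204/3.31 = .0616.
- Mean variance: (.58² + .57² + .64²)/3 = .357.
- r = 1 − .0616/.357 = .827. Rounding in the table allows about .80–.86. An approximate 95% interval (Fisher z, n = 46) is .71–.90.

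**4. Power from the pilot change, 75 per group.**

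| Analysis | r = .5 | r = .827 |
|---|---|---|
| GROUP by TIME, 2 and 296 df | 22% | 56% |
| Six-month value, baseline-adjusted (factor 1 − r²) | 31% | 61% |
| Mean of both visits, baseline-adjusted | 40% | 71% |

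- Unadjusted six-month comparison, which does not depend on r: 0.12/(.58 × √(2/75)) = 1.27, power 24%.
- GROUP by TIME: between-arm differences of 0, .11 and .12 have a sum of squared deviations of .00887. Noncentrality is 37.5 × .00887/(.58² × (1 − r)), which is 1.98 at r = .5 and 5.71 at r = .827.
- Mean of both visits: the mean change is (.11 + .12)/2 = .115. The standard error is .58 × √(2 × .500/75) = .0670 at r = .5 and .58 × √(2 × .230/75) = .0454 at r = .827, giving ratios of 1.72 and 2.53.
- With SD .64, the r = .827 figures for GROUP by TIME and for the mean of both visits fall to 47% and 63%. Taking the full 0.12 at both visits raises the best figure only to 75%.

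**5. r needed for 85% from the pilot change.** About .88 for the baseline-adjusted mean of both visits (.87 if 0.12 is taken at both visits), and about .91 for GROUP by TIME.

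**6. The other two outcomes.** Self-efficacy at .30, baseline-adjusted mean of both visits, r = .3/.5/.7: 68/73/86% (stated 85%). Blood pressure at 5/17.1, same analysis: 66/71/84%. Under GROUP by TIME, with equal differences at three and six months, blood pressure gives 32/44/66% (stated 80%). Both depend on r.

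**The case against.** The strongest reply is that the 85% is not an arithmetic error on the plan's stated inputs. The method uses a baseline correlation, and .33 as a raw-SD difference reaches 85% at r of about .59. That is correct. But .33 would then mean 0.19 points, not the 0.12 in the source the plan cites, so the mismatch stays.

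A reader might infer that .33 must be a standardised change, so that the correlation was counted twice. The documents do not settle this. The distress effect of .70 is close to the baseline-SD value (9.64/14.2 = .68). Applying step 3 to distress with p = .001 gives r of about .24 and a change-SD effect of about .54, not .70. The 52% is therefore one possible reading and not a finding about what the authors did.

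A reader might also infer that the pilot p value rules out the r that 85% needs. At r = .883 the pilot p would have been about .01, not .041, but with 46 women the interval for r runs to about .90. The pilot makes that r less likely; it does not exclude it.

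Finally, the analysis that Section 5.b describes for self-management is a mediation regression, which Section 5.d powers separately (135 women in total, 95%). This limits the consequence. It also means that the test behind the 85% is not named.

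**Conclusion.** The 85% for self-care is not supported by the pilot change given as its basis. With 75 per group and no comparison-arm change, that change gives about 22–40% at r = .5 and 56–71% at r of about .83, depending on the test. These figures assume compound symmetry, SD .58 and an r that is back-calculated, not stated in the plan. Any improvement in the comparison arm, which receives 5000 IU weekly, would lower them.

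Two wider conclusions that a reader might draw do not follow. The self-efficacy and blood pressure figures are not shown to be wrong; their r is simply missing. Nor is the trial shown to be too small: 75 per group is tied to three-month remission, and neither the CES-D power nor the distress power (99% at .70) is disputed here. This is a reporting fault in one component of a secondary outcome, and worth correcting.

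**What to change.** Keep the sample size. In Section 5.d:
- Reconcile .33 with the pilot table, and say which SD standardises each effect.
- Replace the single 85% with power for each outcome, naming the contrast, the test and the assumed r.
- Restate self-care along these lines: *the one-arm pilot change was 0.12 points (0.19–0.21 SD); with 75 per group, SD .58 and no change in the comparison group, power is 22% (GROUP by TIME) to 40% (baseline-adjusted mean of both visits) at r = .5, and 56% to 71% at r = .83*.
- Say that the distress and self-care effects come from a one-arm pilot with no control change subtracted.
- State the r assumed for self-efficacy and blood pressure, or show the range over r.

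The cost is a rewording, with no extra participants and no design change. The drawback is a less favourable stated power for one component of a secondary outcome.
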